COMIRB Protocol

COLORADO MULTIPLE INSTITUTIONAL REVIEW BOARD
[name] [contact] [contact]

Protocol #: 21-2886

Project Title: Opioid Modulation and Neural Reward Activation in Healthy Adults

Principal Investigator: [name]

Version Date: 10/28/21

I. Hypotheses and Specific Aims:

1. Evaluate whether mu-opioid receptor blockade via naltrexone alters reward activation in the ventral striatum. In a study of 10 healthy, moderate drinking adults, we will use a crossover design to examine brain activation during a functional MRI scan during placebo and mu-opioid blockade.

Hypothesis 1. Relative to the placebo scan, participants will show reduced reward-related activation in the ventral striatum during the active medication scan.

2. Evaluate whether mu-opioid receptor blockade alters threat activation in the amygdala. In the same sample and design from Aim 1, we will use the Emotion Regulation Task to assess threat related activation in the amygdala during a functional MRI scan.

Hypothesis 2. Opioid receptor modulation will not affect threat related activation, consistent with naltrexone primarily targeting reward motivation.

3. Examine whether mu-opioid receptor blockade via naltrexone alters valuation of alcohol. In the same sample and study design from Aim 1, we will use the Alcohol Purchase Task to assess subjective value of an alcoholic beverage in order to link opioid-modulation directly to alcohol motivation.

Hypothesis 3. Relative to the placebo session, participants will be willing to pay less money for an alcoholic beverage during the active medication session.

This proposal aims to fill a gap in understanding how endogenous opioid function affects reward response in the brain. One of the leading hypotheses is that individuals who drink to maximize reward are more likely to benefit from naltrexone treatment, and the current proposal would provide evidence for this in a healthy sample. Further, this work could lead to a clinical study of reward-related brain activation and response to naltrexone treatment in adults with an Alcohol Use Disorder. This stands to improve precision medicine approaches to tailor treatments for alcohol use disorder.

II. Background and Significance:

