Our goal is to better understand the neurobiology of reward processing by probing other neurotransmitter systems that interact with dopamine to regulate reward. The objective of this application is to establish whether healthy adults show reduced reward-related activation in the nucleus accumbens when ramped up to steady state dosing with naltrexone. Naltrexone is a mu-opioid antagonist and one of three medications approved by the Food and Drug Administration for the treatment of alcohol use disorder. We will also examine threat processing as a control paradigm to establish that opioid modulation primarily affects reward processing. Since diminishing reward signaling may reduce incentive to seek alcohol, we will also examine a measure of subjective alcohol evaluation. We are prepared to conduct this study based on our expertise in psychopharmacology and functional MRI studies of reward and threat processing as well as psychiatric disorders. This qualified group of investigators will make certain that our research adheres to both neuroscientific theory of reward processing as well as clinical application.

III. Preliminary Studies/Progress Report:

In a currently ongoing study, we have recruited 45 adults to complete the monetary incentive delay task and we have shown a strong main effect of cue type in nucleus accumbens activation ($F_{2,210} = 58.8, p < 0.001$), where activation is greatest during cues to gain \$5 (Figure 1).

[figure not shown]
[figure not shown]

Figure 1. Using the monetary incentive delay task, we found a main effect of cue on nucleus accumbens activation ($F_{2,210} = 58.8$, $p < 0.001$).

IV. Research Methods

A. Outcome Measure(s): There are three outcomes for this study: nucleus accumbens activation to monetary reward, amygdala activation to threat, and subjective alcohol evaluation. For nucleus accumbens activation, we will use percent signal change in response to the cue to earn \$5 during the Monetary Incentive Delay task. For the amygdala response to threat, we will use the percent signal change in response to negative images in the Emotion Regulation task. For the valuation of alcohol, we will use the Alcohol Purchase Task to assess the greatest expenditure on drinks (price paid multiplied by number of drinks).

B. Description of Population to be Enrolled:

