E. Potential Scientific Problems: One challenge of our study is that we will not directly observe naltrexone binding. Directly observing naltrexone's activity would require PET imaging to observe displacement of a tracer that binds to opioid receptors, but we will not do that in this study due to cost and time. Thus, even if we observe behavioral or neural effects, we will not know if naltrexone is acting at that site. However, since we are using a randomized, placebo-controlled design, we can still draw conclusions about naltrexone causing the changes even if the changes may be downstream from naltrexone's direct site of action.

F. Data Analysis Plan: Outcomes will be examined using paired t-tests for two times (active medication, placebo). Functional MRI analysis will be conducted with AFNI software (Cox 1996). Functional images will be time-slice corrected and co-registered with anatomical images. Anatomical images will be non-linearly warped to standard space and an identical transformation will be applied to the functional image. Functional images will be blurred using a 4mm Gaussian kernel and values will be scaled to have a mean intensity of 100. A regression algorithm will be applied including six regressors to account for motion. For the monetary incentive delay task, regressors of interest include the gain, loss, and neutral cue. For the emotion regulation task, regressors of interest include neutral, look, and decrease conditions. For the monetary incentive delay task, activation will be extracted from the nucleus accumbens for each of the three cues. For the emotion regulation task, activation will be extracted from the amygdala for each of the three conditions. As an exploratory analysis, we will conduct whole-brain, voxel-wise analysis.

Sample Size and Power Considerations. In terms of evaluating differences in reward activation between placebo and mu-opioid antagonism conditions, a study of mice estimated a large effect size of mu-opioid antagonism on reward response in the nucleus accumbens, with Cohen's $d > 1.0$ (Walters et al. 2005). A study of kappa-opioid receptor modulation in human reward response measured with functional MRI found a medium to large effect size of Cohen's $d = 0.6$ (Krystal et al. 2020). We specified significance level alpha=.05, two-tailed, and power of 0.8. A sample of 9 adults would provide 80% power to detect an effect size of 1.0 or greater as significant.

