G. Summarize Knowledge to be Gained: We hope to show that reward response is diminished when opioid receptors are blocked in humans. We hope to show that opioid antagonism has specificity for ventral striatal (e.g. nucleus accumbens) activation for rewards. Following this pilot, our goal is to test the effect of naltrexone in adults with an alcohol use disorder. A leading theory is that naltrexone will be more effective in patients who seek alcohol's rewarding effects compared to patients who seek relief of negative symptoms such as anxiety or withdrawal. This would help develop a precision medicine approach to treatment of alcohol use disorder, where clinicians could use reward response as a marker to determine the likelihood of naltrexone's efficacy. We would use this pilot data as part of an R01 application to fund the next study.

H. References:

Adamantidis, Antoine R., Hsing-Chen Tsai, Benjamin Boutrel, Feng Zhang, Garret D. Stuber, Evgeny A. Budygin, Clara Touriño, Antonello Bonci, Karl Deisseroth, and Luis de Lecea. 2011. "Optogenetic Interrogation of Dopaminergic Modulation of the Multiple Phases of Reward-Seeking Behavior." *The Journal of Neuroscience* 31 (30): 10829. <https://doi.org/10.1523/JNEUROSCI.2246-11.2011>.

Bechara, Antoine, Antonio R Damasio, Hanna Damasio, and Steven W Anderson. 1994. "Insensitivity to Future Consequences Following Damage to Human Prefrontal Cortex." *Cognition* 50 (1–3): 7–15.

Bernstein, David P, Laura Fink, Leonard Handelsman, and Jeffrey Foote. 1998. "Childhood Trauma Questionnaire." *Assessment of Family Violence: A Handbook for Researchers and Practitioners*.

Berridge, Kent C, and Morten L Kringelbach. 2008. "Affective Neuroscience of Pleasure: Reward in Humans and Animals." *Psychopharmacology* 199 (3): 457–80.

Brown, Sandra A, Mark G Myers, Linna Lippke, Susan F Tapert, David G Stewart, and Peter W Vik. 1998. "Psychometric Evaluation of the Customary Drinking and Drug Use Record (CDDR): A Measure of Adolescent Alcohol and Drug Involvement." *Journal of Studies on Alcohol* 59 (4): 427–38.

DeWorsop, David, Gina Creatura, Grai Bluez, Halle Thurnauer, Kimberlee Forselius-Bielen, Mohini Ranganathan, Emma Deaso, Jasra Ali Bhat, and Deepak Cyril D'Souza. 2016. "Feasibility and Success of Cell-Phone Assisted Remote Observation of Medication Adherence (CAROMA) in Clinical Trials." *Drug and Alcohol Dependence* 163: 24–30.

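### Hypothesis 2 predicts no threat effect and the plan seeks reward specificity, but separate paired t-tests at n=10 can neither exclude a moderate threat effect nor show that the two drug effects differ

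*Combined protocol and SAP*

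**What the plan says.** Section I states Aim 2 neutrally: "Evaluate whether mu-opioid receptor blockade alters threat activation in the amygdala". Hypothesis 2 beneath it is a null prediction: "Opioid receptor modulation will not affect threat related activation, consistent with naltrexone primarily targeting reward motivation".

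Two other places go beyond Aim 2. Section II says: "We will also examine threat processing as a control paradigm to establish that opioid modulation primarily affects reward processing". Section IV.G says: "We hope to show that opioid antagonism has specificity for ventral striatal (e.g. nucleus accumbens) activation for rewards", and adds that the pilot data will support a grant application for the next study.

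The analysis is in IV.F: "Outcomes will be examined using paired t-tests for two times (active medication, placebo"). The only other analysis there is: "As an exploratory analysis, we will conduct whole-brain, voxel-wise analysis". The document gives no equivalence margin, no interval criterion and no comparison of the drug effect on reward with the drug effect on threat. The sample-size text concerns reward activation only. It gives 9 adults for an effect of 1.0 and also cites an effect of 0.6, from this source: "A study of kappa-opioid receptor modulation in human reward response measured with functional MRI".

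IV.A measures both imaging outcomes in percent signal change. The threat outcome is the amygdala response to negative images, without saying which of the two negative-picture conditions is meant.

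**The concern.** A test of difference can refute a prediction of no effect. When it is non-significant, it says only that the data did not detect an effect, and in a trial of 10 that leaves moderate effects open. Likewise, one significant and one non-significant test do not show that two effects differ, because the comparison between them is never made.

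So the plan has a stated route to refuting Hypothesis 2, but none to supporting it or to supporting specificity. At stake is a possible report of 'reward but not threat' when naltrexone affects both regions alike, carried into the design of the follow-on study in patients with alcohol use disorder.

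**Working it through.** **Inputs from the documents.** n = 10, crossover (section I); two-tailed alpha 0.05; effects of 1.0 and 0.6 (IV.F).

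**Assumed, because the documents do not give them.** The size of any threat effect, the correlation between the two regions' drug effects (0 to 0.5), the ratio of their SDs, any equivalence margin, normal differences and no dropout. Effects are in SDs of the paired drug-placebo difference.

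**The plan's own figure.** For a paired t-test at d = 1.0 the normal approximation gives (1.960 + 0.842)² / 1.0² = 7.85, so 8 people. With the noncentral t distribution, power is 74.8% at n = 9 and 80.3% at n = 10. The stated 9 is therefore one short, but the planned 10 reaches 80%. Nothing below depends on that difference.

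**1. What a non-significant amygdala result excludes.** P(non-significant) comes from the noncentral t with 9 degrees of freedom and noncentrality d√10:
- d = 0.5: 71%
- d = 0.6: 60%
- d = 0.8: 38%
- d = 1.0: 20%

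The 95% CI half-width is t(0.975, 9)/√10 = 2.262/3.162 = 0.72 SD. The 90% half-width is 1.833/3.162 = 0.58 SD. An observed difference of exactly zero is thus compatible with effects up to about 0.7 SD either way.

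**2. How often the 'specific' pattern appears without specificity.** Simulated bivariate normal paired differences, equal standardised effects in both regions, correlations 0, 0.3 and 0.5. P(accumbens significant in the predicted direction, amygdala not):
- both effects 0.6: 24%, 20%, 17%
- both effects 1.0: 16%, 14%, 12%

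**3. The direct contrast.** Take each person's accumbens drug effect minus their amygdala drug effect and apply a paired t-test. If the two effects are equal on the scale used, it favours reward in 2.5% of trials by construction.

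That rate is tied to the scale. Suppose the contrast is in percent signal change, the standardised effects are equal at d, and the amygdala SD is half the accumbens SD (set to 1). The mean contrast is d − 0.5d = 0.5d. Its SD is √(1 + 0.25 − ρ), which is 1.118 at ρ = 0 and 0.866 at ρ = 0.5.
- d = 0.6: standardised contrast 0.27 to 0.35; favours reward in 12% to 16% of trials
- d = 1.0: standardised contrast 0.45 to 0.58; favours reward in 24% to 37% of trials

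The contrast also fires for opposite-sign effects. At +0.6 and −0.6 with equal SDs it is significant in 67% (ρ = 0) to 92% (ρ = 0.5) of trials.

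**4. What the better analyses can deliver at n = 10.** For a reward-only effect of 1.0 with equal SDs, the standardised contrast is 1/√(2(1 − ρ)), that is 0.71 at ρ = 0 and 1.0 at ρ = 0.5. Power is 51% and 80%. If the amygdala SD is double or half the accumbens SD, power ranges from 24% to 90%. Equivalence power (90% CI inside ±margin, true effect zero, integrated over the sample SD) is 7%, 52% and about 80% for margins of 0.5, 0.8 and 1.0 SD.

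**The case against.** - **The plan never says that p > 0.05 will be read as support.** This is correct. Aim 2 asks only whether blockade alters threat activation, and the paired t-test is a valid answer to that. A reader might infer that the sponsor intends to accept the null on non-significance; the documents do not say so. What stands is narrower: section II speaks of establishing the point, and no other route to it is written down.
- **Non-significance is not worthless.** It occurs 95% of the time under no effect and 20% of the time at 1.0, a ratio of about 4.8. At 0.6 the ratio is only 0.95/0.604 = 1.6. So it is too strong to say that the result carries no support at all; the accurate statement is that it cannot exclude moderate effects.
- **The contrast can mislead too.** It is tempting to set 2.5% against 17% to 24%. The two figures describe the same situation only if the regional SDs are equal, and the documents give no SDs. Under the half-SD case above, the percent-signal-change contrast can favour reward more often than the pattern it replaces. This objection stands and shapes the fix.
- **The choice of 0.6.** It comes from a kappa-opioid reward study, so it is an illustration and not a threat estimate. For that reason 1.0 is shown beside it.
- **It is a pilot, and equivalence is out of reach.** That is largely true for narrow margins, and is why estimation should be the default and the equivalence claim optional.

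**Conclusion.** The concern holds in this form: as written, the plan can refute Hypothesis 2, but at n = 10 a non-significant amygdala test cannot exclude moderate effects, and separate tests cannot establish specificity. A true effect of 0.6 SD is missed 60% of the time and one of 1.0 SD 20% of the time. With equal standardised effects the apparently specific pattern arises in 17% to 24% of trials at 0.6 and 12% to 16% at 1.0. These sizes rest on the assumed effects and correlations; the logical gap does not.

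A reader might go further and conclude that the t-test is wrong for Aim 2, or that the reward and alcohol-valuation results are compromised. Neither follows: the test fits Aim 2's question, and the tests of Hypotheses 1 and 3 are untouched. This should be fixed.

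A separate, secondary gap concerns the endpoint. The IV.A wording fits the Look-negative condition, the Decrease condition or their average, since IV.C.b.ii and IV.F have both conditions. With a null prediction, that leaves room to choose after seeing the data.

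**What to change.** In IV.F:

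1. **Hypothesis 2.** Report the amygdala drug-placebo difference with its 95% CI as the assessment. State that p > 0.05 will not be read as support. Allow a claim of no meaningful effect only if the 90% CI lies inside a margin fixed and justified, with its scale, before unblinding. Otherwise report the result as inconclusive.
2. **Specificity.** State that it will not be inferred from one significant and one non-significant test. Base any statement on the accumbens-minus-amygdala contrast of drug effects with its 95% CI, on a scale fixed before unblinding, read alongside the amygdala CI because opposite-sign effects also trigger it. Percent signal change is the natural main scale, since both outcomes already use it. State that its 2.5% error rate holds only for effects equal on that scale, and add a standardised contrast as a sensitivity analysis, noting that it relies on SDs estimated from 10 people.

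Separately, in IV.A, fix the threat condition before unblinding and say whether neutral pictures are the reference. Look-negative is the natural choice, because IV.C.b.ii has participants respond without regulation under Look and reinterpret the picture under Decrease. Decrease can be reported separately.

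**Cost.** Wording only: all three task conditions are already planned to be acquired and extracted. The price is candour. Given the power figures above, the result will often be inconclusive, and the realistic product is an interval for planning the next study.

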- b. MRI. We will conduct a Magnetic Resonance Scan. This will be completed at the Brain Imaging Center (BIC) at the University of Colorado Anschutz Medical Campus. Scanning will be conducted on a Siemens Skyra 3.0 T MR system that is equipped with high performance gradient coils (45mT/m @ 200 T/m/s), a head volume RF coil, and a 32-channel phased-array RF neurovascular coil. The system has a 70 cm bore opening and a weight capacity of 550 lbs. This will be a head-first, supine scan of the brain. Each scan will last one hour. A fMRI run sensitive to blood-oxygenation level-dependent (BOLD) contrast will be collected using T2*-weighted parameters. For anatomical reference, a high-resolution, magnetization prepared rapid gradient echo (MPRAGE) T1-weighted image will be collected during the same session.
- i. **Monetary Incentive Delay task**: The monetary incentive delay task (MID) was developed at the National Institute on Alcohol Abuse and Alcoholism (Knutson et al. 2001). The task has reliably shown that cues signaling a chance to win money recruit activation in the nucleus accumbens, and larger potential gains induce greater activity (Knutson et al. 2001). The task is comprised of three levels of monetary reward (-\$5, +\$0, +\$5). This task reliably recruits nucleus accumbens activation and has a large effect size, with a Cohen's $d > 2.0$. In the MID task, visual stimuli, such as circles, squares, and triangles, are utilized as incentive cues that code the probabilities and magnitudes of outcomes. The first box shows the cue types presented, with circles indicating the potential to win money (gain cue), triangles indicating the potential to lose money (loss cue),

and a square indicating no money will be won or lost (neutral cue). A cue is presented for 500 ms, followed by a fixation cross (2,000 to 2,500 ms) and then the target square (160 to 260 ms), during which the participant is instructed to press a button as quickly as possible to win or avoid losing money. A feedback screen (1,650 ms), in which the top number indicated the amount of money won or lost during that trial and the bottom number indicates the participant's total amount, is presented at the end of each trial.

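### Separate accumbens and amygdala tests cannot show that naltrexone's effect is specific to reward; contrasts between cues within the accumbens should be pre-specified

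*Combined protocol and SAP*

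**What the plan says.** Specificity for reward is a stated aim in three places.

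- Section I, Hypothesis 2: "Opioid receptor modulation will not affect threat related activation, consistent with naltrexone primarily targeting reward motivation".
- Section II, last paragraph: "We will also examine threat processing as a control paradigm to establish that opioid modulation primarily affects reward processing".
- Section IV.G: "We hope to show that opioid antagonism has specificity for ventral striatal (e.g. nucleus accumbens) activation for rewards".

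Section IV.A defines the two outcomes that carry the argument. On the reward side, "For nucleus accumbens activation, we will use percent signal change in response to the cue to earn" 5 dollars in the Monetary Incentive Delay task. On the control side, "For the amygdala response to threat, we will use the percent signal change in response to negative images in the Emotion Regulation task".

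The only test stated, in Section IV.F, is the paired t-test of active medication against placebo on each outcome. The same section models the gain, loss and neutral cues and says that "activation will be extracted from the nucleus accumbens for each of the three cues". It names no contrast between cues, no comparison of the two regions and no equivalence margin for the amygdala.

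**The concern.** The two outcomes differ in much more than reward versus threat. One is the accumbens during a speeded button-press task for money (Section IV.C.b.i). The other is the amygdala while participants view and rate pictures (Section IV.C.b.ii). Suppose naltrexone lowers the accumbens response to any cue with money at stake, or lowers accumbens responses in general. The two planned tests would look just as they would under an effect confined to gain cues. No further analysis of the amygdala data removes this, because the missing comparison lies within the accumbens.

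What is at stake is the interpretation. The test of Hypothesis 1 is unaffected: it can still show that naltrexone lowers the accumbens response to the gain cue. The further step, that the effect is on reward in particular, has no planned support. Section IV.G intends these pilot data for a grant application and relates them to a theory about patients who drink for reward rather than for relief.

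**Working it through.** **Inputs from the documents.** 10 participants in a crossover (Section I); two-sided alpha 0.05 and 80% power; a standardised effect of 1.0, taken from a mouse study, and of 0.6, from a human imaging study of kappa-opioid modulation (all in the sample-size paragraph of Section IV.F).

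**Assumptions not in the documents.** Independent noise in the accumbens and amygdala tests; no dropout, period or carryover effect; equal SDs for the drug effects on the gain and loss cues; a correlation rho between those two drug effects, shown over 0 to 0.75.

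**1. The plan's own figure.** Power of a paired t-test comes from the noncentral t with n − 1 degrees of freedom and noncentrality d√n. The plan states that 9 adults give 80% power at d = 1.0. The exact calculation gives 74.8% at n = 9 and 80.3% at n = 10. The planned 10 therefore meets the target at d = 1.0. At d = 0.6, power with n = 10 is 39.6%.

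**2. The pattern that would suggest specificity.** Take a true accumbens effect of size d on the gain cue and no amygdala effect.

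P(accumbens significant, amygdala not) = power(d) × 0.95

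- d = 1.0: 0.803 × 0.95 = 0.763, or 76%
- d = 0.6: 0.396 × 0.95 = 0.376, or 38%

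The loss cue does not enter this expression. The probability is the same whether the loss response is untouched or falls as much as the gain response, so the planned tests do not discriminate between the two.

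A non-significant amygdala result is also weak evidence in itself. A true amygdala effect of 0.6 would be non-significant in 1 − 0.396 = 60% of trials.

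**3. What gain minus loss would add.** If the drug effect on loss is a fraction f of that on gain, the standardised effect on the contrast is

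d_c = d(1 − f) / √(2(1 − rho))

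Power at n = 10:

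| d | f | rho = 0 | rho = 0.5 | rho = 0.75 |
|---|---|---|---|---|
| 1.0 | 0 (gain only) | 51.4% | 80.3% | 97.7% |
| 0.6 | 0 (gain only) | 22.5% | 39.6% | 66.7% |
| 1.0 | 0.5 | 17.1% | 29.3% | 51.4% |

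The 95% interval half-width, in SDs of the drug effect on one cue, is 2.262 × √(2(1 − rho)) / √10. This is about 1.0, 0.7 and 0.5 at the three correlations.

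**4. How far a positive contrast can be trusted.** If gain and loss fall by the same absolute amount (f = 1), a significant fall in gain minus loss occurs in 2.5% of trials, one tail of the test. Requiring it together with the pattern in step 2 gives about 2% by simulation. That figure depends on equal absolute falls. Section III reports that accumbens activation is greatest for the 5-dollar gain cue, so if naltrexone damped every accumbens response in proportion, gain would fall more than loss. If the loss response were half the gain response (an assumption), the third row of the table applies: the contrast would be significant in 17% to 51% of trials although the effect was not specific to gain.

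**The case against.** The strongest reply is that the plan contains no rule turning a significant accumbens result and a non-significant amygdala result into a claim of specificity. Hypothesis 2 speaks only of consistency, Section II says primarily, and Section IV.G expresses a hope. That stands. A reader might infer from the 76% that the trial would report a false specificity claim that often. The documents do not support this: 76% is the probability of a pattern, and under the assumed truth both of its component results are correct. Even so, Section II says the control is there to establish the point, and no other evidence for it is planned.

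A reader might also infer that the loss cue would settle the matter. It would not. Participants press quickly to avoid losing money, so the loss cue is itself an incentive cue. Steps 3 and 4 show that the contrast may be underpowered and can also fall under proportional damping. The neutral cue is needed too: gain minus neutral bears on incentive against a general accumbens or signal effect, and gain minus loss on gain against incentive of either sign.

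Two further points stand in part. The threat task is a reasonable check on global sedation, since sleepiness (a listed side effect) would have to blunt the accumbens and spare the amygdala to mislead. The claim in Section IV.G is also partly regional, and for that part an across-region control is relevant. Neither supplies the comparison between cues that the reward part of the claim needs.

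**Conclusion.** The concern holds as a gap between the stated aim and the planned evidence. Region, task and stimulus are confounded with valence. The pattern that would suggest reward specificity has the same probability under a gain-only effect and under one shared with the loss cue: 76% at d = 1.0 and 38% at d = 0.6, assuming 10 pairs, no amygdala effect and independent noise.

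Contrasts between cues within the accumbens are better evidence, and their inputs are already extracted. They can support specificity but not prove it, and with 10 participants a non-significant contrast is inconclusive. It should not be read as showing a general effect. Their power depends on a correlation that the documents do not give.

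**What to change.** Add to Section IV.F wording such as:

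> In the nucleus accumbens, the active-versus-placebo difference will be estimated for each cue and, by paired comparison, for gain minus neutral and gain minus loss percent signal change, each with a 95% confidence interval. The effect of naltrexone will be described as larger for gain than for neutral or loss cues only if the relevant contrast supports it. A non-significant contrast will be treated as inconclusive.

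Keep the amygdala result as a secondary, across-region control. Soften the verb establish in Section II and the specificity statement in Section IV.G to match. State the limits alongside: the loss cue is an incentive cue, and proportional damping would also lower gain minus loss.

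The cost is a few lines of analysis text and one or two extra paired comparisons on values already extracted, with no new data or visits. The downside is that a specificity claim becomes harder to make.
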